10.3.1.3 Disease Response Assessment Criteria

Patients will have radiological disease assessments performed every 6 weeks (+/-3 days) (Week 6, Week 12, etc.) during study treatment through week 36 or until unequivocal progressive disease. If progressive disease has not occurred by week 36, radiological assessments will be then be done every 9 weeks (+/-3 days) until unequivocal progressive disease. Images should be kept to the calendar schedule and not be delayed for missed study drug administration.

Partial or complete response should be confirmed by a repeat tumor imaging assessment not less than 4 weeks from the date the response was first documented. The tumor imaging for confirmation of response may be performed at the earliest 4 weeks after the first indication of response, or at the next scheduled scan if on a 6 week schedule, whichever is clinically indicated.

In subjects who discontinue study therapy without documented unequivocal progressive disease, every effort should be made to continue monitoring their disease status by tumor imaging every 6 weeks until (1) unequivocal progressive disease (2) death, or (3) the end of the study, whichever occurs first. All scans will be submitted (electronically whenever possible) to a central core radiologic laboratory within 3 days of being performed, where they will immediately be reviewed for readability. The lab will contact the site should any issues or questions arise.

Disease progression is determined locally, not by the central core radiologic lab. Scans from patients who were determined by the Investigator to have a response to treatment (CR or PR) will be reviewed by the core radiologic laboratory to confirm response. The lab will collect and hold all scans should the sponsor decide to have them read to confirm PFS outcomes.

Scans from non-responders may also be reviewed by the core radiologic laboratory at the direction of the Sponsor.

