Patients will remain on study treatment until unequivocal progression of disease (PD), intolerable toxicity, or one of the other study withdrawal criteria is met (Protocol [Section 11](#)). Patients with radiographic progression only, as defined by RECIST 1.1 should continue on study treatment until unequivocal progressive disease is determined as defined by irRECIST, at the discretion of the investigator. After study treatment discontinuation, patients will complete an End of Treatment (EOT) visit within 7 days after the last study drug dose and a Safety Follow-up (F/U) visit 30 days (+/- 3 days) later. After completion of the 30-day (+/- 3 days) Safety F/U visit, patients who have not experienced PD, are to be followed every 6 weeks for a clinic visit and radiological imaging until unequivocal progressive disease or until study week 36, whichever occurs first. If PD has not been documented at that time, patients will be followed every 9 weeks for radiological imaging until unequivocal progressive disease, death or end of the study whichever occurs first. Patients who discontinue study treatment for PD will be contacted every 3 months for survival status and post study therapies until death or closure of the study by the Sponsor.

Phase 1b / Dose Determination Phase: Up to 18 patients are expected to be enrolled in the Dose Determination Phase of the study which employs a classical 3+3 design, with the determination of DLT and the MTD and/or RP2D based on entinostat in combination with atezolizumab in C1. All dose cohorts will receive entinostat orally at the assigned dose on Days 1, 8 and 15 along with atezolizumab 1200 mg on Day 1 of a 21 day cycle. Dose group 1 will include 3-6 patients who will receive entinostat at a starting dose of 5 mg. If the entinostat 5 mg dose exceeds the MTD, then a 3 mg dose of entinostat (Dose Group

-1) will be evaluated in the same manner. If the entinostat 3 mg dose exceeds the MTD, then a 2 mg dose of entinostat (Dose Group -2) will be evaluated in the same manner. All patients within a cohort are to complete C1, have safety assessments performed through C2D1, and be assessed for DLT before enrollment of additional patients may commence. If <33% patients within a cohort have a DLT (i.e., <2 of 6), then enrollment of the Phase 2 Expansion cohort may commence with approval from the Syndax Study Physician.

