Blood sample for atezolizumab serum biomarker		X ¹³			X ¹³	X ¹³	X ¹³	X ¹³		
Blood sample for atezolizumab plasma biomarker		X ¹³			X ¹³	X ¹³	X ¹³	X ¹³		
Blood sample for protein lysine acetylation ¹³		X ¹⁴		X ¹⁴						
Tissue sample biopsy for immune correlates (also archival tissue when available)	X ¹⁵					X ¹⁵		X ¹⁵		
Entinostat self-administration		Self-administered weekly starting on C1D1; C1D1 ≤3 business days of								

Procedure	Screening (D -21 to -1)	Combination Therapy						EOT (≤7 days of last study drug dose)	Safety F/U (≤30 days of EOT)	Post- Study F/U ¹
		C1			C2		≥C3			
		D1	D8	D15	D1	D15	Day 1			
Visit Window	-	-	±1D	±1D	±3D	±3D	±3D	±3D	±3D	±5D
enrollment										
Atezolizumab administration ¹⁶		X			X		X			
Blood sample for entinostat pharmacokinetics ¹⁷		X ¹⁷	X ¹⁷	X ¹⁷	X ¹⁷					
Blood sample for atezolizumab pharmacokinetics and anti-therapeutic antibodies ¹⁸		X ¹⁸			X ¹⁸			X ¹⁸		X ¹⁸
Pre-treatment/concomitant medications	X	X	X	X	X	X	X	X	X	
Adverse events	X	X	X	X	X	X	X	X	X	
Study drug compliance assessment		X	X	X	X	X	X	X	X	

¹ After the Safety F/U visit, patients who have not experienced PD are followed (including radiological assessments) q6 weeks (+/- 3 d) through study week 36 and then every 9 weeks (+/- 3 d) thereafter until unequivocal PD. Thereafter, they are contacted q3 months until death or study closure for information on PD, alternate treatments and survival status.

² If the screening complete PE was performed within 7 days before C1D1, then a symptom-directed examination may be performed at enrollment.

³ An ECG is to be performed pre-dose on C3D1 (- 3d) and then every 3 cycles (- 3d) thereafter. An ECG may be repeated anytime, as clinically indicated.

⁴ Also performed if fluid retention occurs

⁵ Performed only if last scan was performed >28 days before C1D1

⁶ Patients will have radiological disease assessments performed every 6 weeks (+/- 3 d) through week 36 (Week 6, 12, 18, etc.) and then q9 weeks (+/- 3 d) hereafter during treatment and for patients who have not yet progressed when discontinuing study treatment, until progression based on this schedule.

- Partial or complete response should be confirmed by a repeat tumor imaging assessment at the earliest 4 weeks after the first indication of response, or at the next scheduled scan if on a 6 week schedule, whichever is clinically indicated.

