Blood for immune correlates is to be collected pre-dose on each of C1D1, C2D1, C2D15, C3D1 and at the end of treatment. Blood for protein lysine acetylation is to be collected pre-dose on C1D1 and C1D15. Patients will have radiological disease assessments performed every 6 weeks (+/-3 days) (Week 6, Week 12, etc.) beginning at C1D1, during study treatment through week 36 or until progressive disease. If progressive disease has not occurred by week 36, radiological assessments will then be done every 9 weeks (+/-3 days) until progressive disease. If a patient comes off study for reasons other than progressive disease, radiological assessments will continue at 6 week intervals until what would have been study week 36 and then switch to a 9 week interval, until progressive disease is radiologically documented. Disease will be assessed by computed tomography (CT), magnetic resonance imaging (MRI), and bone scans, as appropriate, and response will be assessed by the Investigator using irRECIST. The same imaging modality should be employed for all follow-up scans as was used at baseline.

Safety will be assessed during the study by documentation of AEs, clinical laboratory tests, physical examination, vital sign measurements, ECGs, and Eastern Cooperative Oncology Group (ECOG) performance status.

Within 7 days of the last dose of study treatment, all patients will complete an End of Treatment (EOT) visit, and a Safety Follow-up (F/U) visit will be required 30 days (+/- 3 days) thereafter.

After completion of the 30-day F/U visit, patients who have experienced progressive disease are to be contacted every 3 months thereafter for survival status and information regarding treatment regimens, until death or closure of the study by the Sponsor. Those patients who have not experienced progressive disease, will continue radiological disease assessments as noted above.

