9.9 Treatment Duration

The duration of treatment for this study is expected to be 1 year. Patients may remain on study until unequivocal progressive disease, unacceptable toxicity, or another treatment withdrawal criteria is met per Protocol [Section 11](#). Study patients with evidence of radiological progressive disease who meet the criteria set forth in Protocol [Section 10.3.2](#) for “Treatment After Initial Radiological Progression”, should continue treatment and be followed according to irRECIST as described in [section 10.3.2](#). Any questions should be directed to the Medical Monitor.

If a patient permanently discontinues either study drug (entinostat/placebo or atezolizumab), the patient will be taken off study treatment and followed for progressive disease per protocol guidelines, or overall survival should progressive disease have been previously determined on study. Patients will receive standard of care outside the auspices of this study at the Investigator's discretion.

After discontinuation of study treatment, patients will complete an EOT visit within 7 days (+/- 3 days) after the last study drug dose and a Safety F/U visit 30 days (+/- 3 days) thereafter.

After completion of the 30-day Safety F/U visit, patients who have not experienced PD are to continue to undergo radiological assessments every 6 weeks until study week 36, and then every 9 weeks thereafter until progressive disease. The purpose of the post-treatment follow-up is to ascertain the duration of PFS for all patients in the study.

After they experience PD, surviving patients are to be contacted every 3-months for documentation of subsequent therapies and survival until closure of the study or patient death, whichever should occur first.

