10. STUDY TESTS AND OBSERVATIONS

After provision of written informed consent, patients will be screened for study eligibility within 21 days before study enrollment. Patients who are determined to be eligible based on screening assessments and who are enrolled, **must begin treatment (C1D1) with entinostat/placebo in combination with atezolizumab within 3 business days of the date of enrollment/randomization.**

A cycle is 21 days in length. Patients will attend study center visits and undergo study evaluations on C1D1, C1D8, and C1D15; D1 and D15 of C2; and on D1 of each cycle thereafter.

Patients will have radiological disease assessments during screening and then during treatment and follow-up every 6 weeks (+/-3 days) (Week 6, Week 12, etc.) through week 36 and then every 9 weeks (+/- 3 days) thereafter until unequivocal progressive disease. This schedule is to be followed both during study treatment and following discontinuation of study treatment in the absence of progressive disease.

After discontinuation of study treatment, patients will complete an EOT visit within 7 days (+/- 3 days) after the last study drug dose and a Safety Follow-up visit 30 days (+/- 3 days) thereafter. After completion of the 30-day Safety F/U visit, patients who have not experienced PD are to continue to undergo radiological assessments every 6 weeks through week 36 and then every 9 weeks thereafter until unequivocal progressive disease. The purpose of the post-treatment follow-up is to ascertain the duration of PFS for all patients in the study. After progressive disease, surviving patients are to be followed every 3-months for documentation of subsequent therapy and survival until closure of the study or death.

Protocol-required tests, observations, and procedures are summarized in [Table 1-1](#).

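### Section 10.3.1.3 keeps off-treatment patients on 6-weekly scans after week 36, where every other section moves them to 9 weeks; this changes when progression is seen and which visits count as missed

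*Protocol*

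**What the plan says.** Section 10.3.1.3 contains two schedules. For patients on treatment it gives 6-weekly imaging to week 36, after which "radiological assessments will be then be done every 9 weeks (+/-3 days) until unequivocal progressive disease". For patients who discontinue without documented progression it then asks for monitoring "by tumor imaging every 6 weeks until (1) unequivocal progressive disease", or until death or the end of the study if either comes first. That second sentence has no switch at week 36.

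Every other place that sets the off-treatment interval includes the switch:

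- Synopsis, for patients without progression by week 36: "patients will be followed every 9 weeks for radiological imaging until unequivocal progressive disease, death or end of the study whichever occurs first".
- Table 1-1, footnote 1: "q6 weeks (+/- 3 d) through study week 36 and then every 9 weeks (+/- 3 d) thereafter until unequivocal PD". Footnote 6 applies the same pattern during treatment and to patients who stop before progressing.
- Section 6.1: "radiological assessments will continue at 6 week intervals until what would have been study week 36 and then switch to a 9 week interval".
- Section 9.9, after the safety follow-up visit: "every 6 weeks until study week 36, and then every 9 weeks thereafter until progressive disease".
- Section 10, after setting out 6 then 9 weeks: "This schedule is to be followed both during study treatment and following discontinuation of study treatment in the absence of progressive disease".
- Section 10.3.1.1: a patient who comes off study for a reason other than progression stays on the same schedule.

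SAP 6.1 censors a progression or death that follows two or more consecutive missed scheduled assessments, but does not state the schedule. SAP Table 2, sensitivity analysis 5, places an assumed progression at the next scheduled scan and fixes that at 42 days after the last one.

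**The concern.** Investigator-assessed PFS is the primary endpoint, so the rule for when scans are taken is part of how the endpoint is measured. Read literally, Section 10.3.1.3 makes the interval after week 36 depend on whether the patient is still on treatment.

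Treatment status could differ by arm. Under Sections 9.9 and 9.10, permanently stopping either drug takes the patient off study treatment. Section 12.1.1 reports more toxicity with entinostat than with placebo in an earlier randomized breast cancer trial (for example fatigue 48% vs 26%, neutropenia 30% vs 0%).

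Two things are at stake: the date on which progression is recorded, and whether a late progression counts as an event or is censored. The second is left to whoever decides which schedule defines a missed visit.

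**Working it through.** The plan states no figure to reproduce. The contradiction is textual, and the arithmetic below only sizes it.

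**Number of scans.** Counting from week 36 to week 72, the 6-week rule gives scans at weeks 42, 48, 54, 60, 66 and 72 (6 scans). The 9-week rule gives weeks 45, 54, 63 and 72 (4 scans). The ratio is 6/4 = 1.5.

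**Shift in detection.** Take both schedules as running from the week 36 scan. The pattern repeats every 18 weeks.

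| True progression (weeks) | Length | Seen, 6-week rule | Seen, 9-week rule | Effect of 6-week rule |
|---|---|---|---|---|
| 36–42 | 6 | 42 | 45 | 3 weeks earlier |
| 42–45 | 3 | 48 | 45 | 3 weeks later |
| 45–48 | 3 | 48 | 54 | 6 weeks earlier |
| 48–54 | 6 | 54 | 54 | none |

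With progression spread evenly over the 18 weeks, the mean shift is (6×3 − 3×3 + 3×6 + 6×0)/18 = 27/18 = 1.5 weeks earlier. This equals the difference in mean waiting time, 9/2 − 6/2. With exponential PFS at the planned medians, the mean delays to the next scan are 3.1 and 4.7 weeks (median 7 months) and 3.1 and 4.8 weeks (median 4 months), a difference of about 1.6 weeks.

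**Effect on the censoring rule.** Take a patient off treatment by week 36, on no new therapy, scanned at week 36 and next at week 54, when progression is seen.

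- 6-week schedule: weeks 42 and 48 were missed. That is two consecutive assessments, so PFS is censored at week 36.
- 9-week schedule: only week 45 was missed, so PFS is an event at week 54.

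In general, two missed visits leave a gap of 3×6 = 18 weeks on one schedule and 3×9 = 27 weeks on the other.

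**Sensitivity analysis 5.** 42 days is 6 weeks. A 9-week interval is 63 days, so after week 36 the fixed step agrees only with the Section 10.3.1.3 sentence.

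**How many patients.** Week 36 is 36×7/30.4375 = 8.28 months. Under exponential PFS with medians of 4 and 7 months (Section 13.1.2):

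- control: 0.5^(8.28/4) = 0.238, and 35 × 0.238 = 8.3 patients
- entinostat: 0.5^(8.28/7) = 0.441, and 35 × 0.441 = 15.4 patients
- total: about 24 of 70 progression-free at week 36

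Only those of the 24 who are off treatment and have not started new anticancer therapy are exposed. The documents do not give that share. For scale only, an assumed 10% to 30% off treatment gives 2.4 to 7.1 patients, before removing those on new therapy.

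**The case against.** The strongest reply is that the governing schedule is not in real doubt. Six other places agree, Section 10 says outright that one schedule covers both situations, and Section 10.3 wants tumor assessments kept to the calendar whatever happens to dosing. The sentence in Section 10.3.1.3 is worded as an aim rather than a requirement, and nothing suggests that a treatment-dependent interval was intended. All of this stands. It makes the sentence a drafting inconsistency rather than a design decision, and it shows which way the text leans. It does not remove the sentence, which sits in a section that sites consult on disease assessment.

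A second reply is that the analysis plan already limits the damage. The primary analysis censors patients who start new anticancer therapy without progression. Sensitivity analysis 3 in SAP Table 2 censors patients who stop treatment for other reasons at their last scan up to discontinuation, which removes the scans in question. Analysis 2 drops the missed-visit censoring. The protocol also plans sensitivity work on departures from scheduled scan times. These would help show an effect, but they do not settle which schedule the primary analysis should use to count missed visits.

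A reader might infer that PFS ascertainment is biased between arms. The documents do not support that. It would require sites to follow this one sentence over the others, patients to be off treatment, progression-free and on no new therapy after week 36, and their number to differ by arm. No discontinuation rates are given. If more entinostat patients were off treatment, earlier average detection would tend to work against entinostat, so it would not inflate a positive result.

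**Conclusion.** The inconsistency is real and minor. One sentence in Section 10.3.1.3 conflicts with the synopsis, Table 1-1 and Sections 6.1, 9.9, 10 and 10.3.1.1 on the off-treatment scan interval after week 36. The schedules agree up to week 36.

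If the sentence were followed, detection would move by between 6 weeks earlier and 3 weeks later, on average 1.5 weeks earlier. Some late progressions could change between event and censored. The 3-week gap between the two intervals might be taken as the largest possible shift; the scan calendars show that it is not. Nor is the 6-weekly imaging without end, since it stops at progression, death or study end.

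The effect on the primary result is probably small, and a difference between arms is conditional on different rates of discontinuation without progression. This rests on exponential PFS at the planned medians, on both schedules running from the same scan, and on an off-treatment share that the documents do not report.

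**What to change.** 1. Reconcile the off-treatment sentence in Section 10.3.1.3 with the synopsis, Table 1-1 footnotes 1 and 6, and Sections 6.1, 9.9, 10 and 10.3.1.1, so that one calendar schedule applies on and off treatment. The difference after week 36 then disappears.
2. In SAP 6.1, cite that schedule as the basis for counting missed assessments.
3. In SAP Table 2, sensitivity analysis 5, replace the fixed 42 days with the scheduled interval in force at the time of the last scan.

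The cost is one protocol sentence and two short SAP edits. Sample size, scan burden under the common schedule and the analysis method do not change.

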10.3.2 Treatment after Initial Radiologic Progression

Immune related RECIST (irRECIST) (Appendix 4) will be utilized to account for the unique tumor response characteristics seen with atezolizumab treatment. Immunotherapeutic agents such as atezolizumab may produce antitumor effects by potentiating endogenous cancer-specific immune responses. The response patterns seen with such an approach may extend beyond the typical time course of responses seen with cytotoxic agents, and a clinical response may manifest after an initial increase in tumor burden or even the appearance of new lesions.

Patients with a first radiological evidence of progressive disease, should continue on study treatment, at the discretion of the investigator, until confirmed progressive disease is determined per irRECIST in a subsequent scan. Therefore, the following process for assessing radiological progressive disease will be used in this study:

1. If radiologic imaging demonstrates initial evidence for PD, tumor assessment should be repeated at the earliest of 4 weeks, or preferably on the study schedule of 6 weeks, in order to confirm PD. Treatment on-study may be continued while awaiting radiologic confirmation of progression. This clinical decision should be based on the patient's overall clinical condition, including performance status, clinical symptoms, and laboratory data.
2. Specifically, it is recommended that patients continue to receive study drug while waiting for confirmation of PD if they are clinically stable as defined by:
 - Absence of signs and symptoms indicating PD.
 - No decline in ECOG performance status.
 - Absence of rapid PD.
 - Absence of progressive tumor at critical anatomical sites (e.g., cord compression) requiring urgent alternative medical intervention.

As per irRECIST, if repeat imaging does not show irPD, then PD by irRECIST will not have been confirmed and treatment may be continued. If repeat imaging confirms irPD, PD will have been confirmed and the patient will be discontinued from study treatment.

Table 10-2 Imaging and Treatment After 1st Radiologic Evidence of PD

	Clinically Stable		Clinically Unstable	
	Imaging	Treatment	Imaging	Treatment
1 st radiologic evidence of PD	Repeat imaging at next scheduled time point to confirm PD	May continue study drug at the Investigator's discretion while awaiting confirmatory scan by site	Repeat imaging at next scheduled time point to confirm PD per physician discretion only	Discontinue treatment
Repeat scan confirms irPD	No additional imaging required	Discontinue treatment	No additional imaging required	N/A
Repeat scan shows SD, PR or CR (per irRECIST)	Continue regularly scheduled imaging assessments	Continue study drug at the Investigator's discretion	Continue regularly scheduled imaging assessments	May restart study drug if condition has improved and/or clinically stable per Investigator's discretion

NOTE: If a subject has confirmed radiographic progression (i.e. 2 scans at least 4 weeks apart demonstrating progressive disease), but the subject is achieving a clinically meaningful benefit, and there is no further increase in the tumor burden at the confirmatory tumor imaging, an exception to continue treatment may be considered following consultation with the Medical Monitor. In this case, if treatment is continued, tumor imaging should continue to be performed following the study required intervals per [Table 1-1](#).

When feasible, patients should not be discontinued until PD is confirmed. However, patients that are deemed clinically unstable are not required to have repeat imaging for confirmation of PD and should come off study treatment.

